# EIRB Protocol Template (Version 1.9)

## 1.0 General Information

**\*Please enter the full title of your study:**

Comparison of Intramuscular Ketorolac at Two Single-Dose Regimens for Treatment of Acute Musculoskeletal Pain in a Military Emergency Department: A Randomized Controlled Non-Inferiority Trial

**\*Please enter the Protocol Number you would like to use to reference the protocol:**

Intramuscular Ketorolac at Two Single-Dose Regimens

\* This field allows you to enter an abbreviated version of the Protocol Title to quickly identify this protocol.

**Is this a multi-site study (i.e. Each site has their own Principal Investigator)?**

No

**Does this protocol involve the use of animals?**

Yes  No

**3.4 If applicable, please select the Designated Site Approval(s):**

Add the name of the individual authorized to approve and sign off on this protocol from your Site (e.g. the Site Chair).

## 4.0 Project Information

**4.1 \* Has another IRB/HRPP reviewed this study or will another IRB/HRPP be reviewing this study?  
If Yes, answer the questions according to the IRB/HRPP Determination.**

Yes  No

IRB Name	Review Date	Determination
No records have been added		

**4.2 \* Is this a research study or a Compassionate Use/Emergency Use/HUD project?**

Yes  No

**4.3 What type of research is this?**

- Biomedical Research
- Clinical trial (FDA regulated)
- Behavioral Research
- Educational Research
- Psychosocial Research
- Oral History
- Other

**4.4 Are you conducting this project in pursuit of a personal degree?**

Yes  No

**4.6 \* Is this human subjects research? (As defined by 32 CFR 219)**

**Human subject means a living individual about whom an investigator (whether professional or student) conducting research:**

(i) Obtains information or biospecimens through intervention or interaction with the individual, and uses, studies, or analyzes the information or biospecimens; or  
 (ii) Obtains, uses, studies, analyzes or generates identifiable private information or identifiable biospecimens.

Yes  No

#### 4.7 \* Do you believe this human subjects research is exempt from IRB review?

Yes  No

### 5.0

#### Personnel Details

##### 5.1 List any Research Team members without EIRB access that are not previously entered in the protocol:

No records have been added

##### 5.2

#### Will you have a Research Monitor for this study?

Yes  
 No  
 N/A

### 6.0

#### Data/Specimens

##### 6.1 Does the study involve the use of existing data or specimens only (no interaction with human subjects)?

Yes  No

## 7.0

### Funding and Disclosures

#### 7.1 Source of Funding:

Funding Source	Funding Type	Amount
No records have been added		

Total amount of funding:

0

#### 7.2 Do you or any other Investigator(s) have a disclosure of a personal interest or financial nature significant with sponsor(s), product(s), instrument(s) and/or company(ies) involved in this study?

Yes  No

If Yes, complete and attach Conflict of Interest forms for all key personnel

## 8.0

### Study Locations

#### 8.1 Is this a collaborative or multi-site study? (e.g., are there any other institutions involved?)

Yes  No

#### 8.2 Study Facilities and Locations:

Institution	Site Name	Site Role	FWA or DoD Assurance Number	Assurance Expiration Date	Is there an agreement?	IRB Reviewing for Site
No records have been added						

Other:

Other Institution Site	Site Role	FWA or DoD Assurance Number	FWA or DoD Expiration Date	Is there an agreement?	IRB Reviewing for Site
No records have been added					

#### 8.3 Are there international sites?

Attach international approval documents, if applicable, when prompted. Note: Ensure local research context has been considered

Yes  No

#### 8.4 Is this an OCONUS (Outside Continental United States) study?

Yes  No

Select the area of responsibility:

Have you obtained permission from that area of responsibility? (This is a requirement prior to study approval)

Yes  No

## 9.0

### Study Details

#### 9.1 Key Words:

Provide up to 5 key words that identify the broad topic(s) of your study

Ketorolac, intramuscular, analgesia, pain, emergency department

#### 9.2 Background and Significance:

Include a literature review that describes in detail the rationale for conducting the study. Include descriptions of any preliminary studies and findings that led to the development of the protocol. The background section should clearly support the choice of study variables and explain the basis for the research questions and/or study hypotheses. This section establishes the relevance of the study and explains the applicability of its findings

Ketorolac tromethamine is one of the most commonly used parenteral analgesics in the emergency department (ED) for the treatment of moderate to severe pain. It is a nonsteroidal anti-inflammatory drug (NSAID) that belongs to a group of non-opioid analgesics that primarily inhibit the activity of both cyclooxygenase-1 (COX-1) and cyclooxygenase-2 (COX-2) enzymes and block the synthesis of prostaglandins and thromboxanes. It has high COX-1 enzyme selectivity, a half-life of 2.4 to 8.6 hours, and is extensively metabolized in the liver and eliminated through the kidneys.

There is limited evidence demonstrating increased analgesic effect with higher doses of ketorolac. Kantorovich et al. concluded that 10 mg is the analgesic ceiling dose for both intravenously and intramuscularly administered ketorolac. The analgesic ceiling is the dose of a drug beyond which further dosage increase results in no additional analgesic effect. Staquet demonstrated in cancer patients with moderate to severe pain that a dose of 10 mg delivered via intramuscular injection (IM) was effective in relieving pain and associated with fewer side effects. Further studies have corroborated these findings. A study conducted by Reuben and colleagues studied different doses of intravenous (IV) ketorolac as an adjunct to morphine sulfate in patients who had spinal stabilization surgery. The results suggest that increasing the doses of ketorolac did not increase the efficacy of the drug, and the 7.5 mg dose had the same efficacy as larger doses. Minotti et al performed a double-blinded study that compared the analgesic effects of ketorolac 10 mg IM, ketorolac 30 mg IM, and diclofenac 75 mg IM in 180 cancer patients. The results demonstrated no difference in pain relief among all three groups. Other studies have also demonstrated similar results for postoperative patients.

The most recent study comparing different ketorolac dosing regimens on emergency department patients also support previous studies demonstrating an analgesic ceiling. The most recent of which is a study conducted by Motov et al. who evaluated the analgesic efficacy of three different doses of IV ketorolac including 10 mg, 15 mg, and 30 mg doses in 240 emergency department patients who suffered from acute pain. This randomized, double-blind clinical trial determined similar efficacy in patient pain reduction scores across all three doses of ketorolac within 30 minutes.

Despite studies indicating the non-inferiority of a lower parenteral dose of ketorolac, it continues to be dosed higher than the proposed analgesic ceiling dose, particularly in the emergency department. Soleyman-Zomalan and colleagues investigated the patterns of ketorolac dosing conducted by emergency physicians, and their data indicated that ketorolac was prescribed above the 10 mg ceiling dose in 97% of patients receiving intravenous doses and 96% of patients receiving intramuscular doses. This pattern of emergency department prescribing may be explained by the fact that 10 mg is lower than the parenteral dosing regimen recommended in emergency medicine textbooks and by the Food and Drug Administration (approved doses of 30 mg intravenously and 60 mg intramuscularly for patients younger than 65 years). Additionally, ketorolac is stored and packaged by the manufacturer in 15 mg/mL, 30 mg/mL, and 60 mg/2mL vials, which complicates alternate dosing calculations of ketorolac.

Current standard of practice for the treatment of acute musculoskeletal pain is provider dependent. Additionally, it depends on the chief complaint, examination, and clinical picture. For non-critical acute MSK patients options are generally oral NSAIDs and IM NSAIDs. It is medical standard of care to not prescribe or administer opioids for musculoskeletal pain in the ED, unless the injury is severe (such as a long bone fracture or dislocation of a large joint). However, even in these circumstances nerve blocks and hematoma blocks may be attempted to attenuate the pain prior to administration of IV or IM opioids. Therefore, non-opioid analgesics, such as acetaminophen or Toradol are logically the first analgesics used by many providers to control the pain caused by minor musculoskeletal injuries. In general, the most common dosages for intramuscular administration of Toradol is either 30 mg or 60 mg. The most common intravenous dosing for Toradol is 15 mg or 30 mg.

#### 9.3

##### **Objectives/Specific Aims/Research Questions:**

Describe the purpose and objective(s) of the study, specific aims, and/or research questions/hypotheses

**Purpose:** The purpose of this study is to evaluate the effectiveness of 15 mg ketorolac versus 60 mg ketorolac injected intramuscularly for the treatment of acute musculoskeletal pain in military emergency department patients.

The alternative hypothesis is that 15 mg intramuscular ketorolac will be non-inferior when compared to 60 mg intramuscular ketorolac for the treatment of acute musculoskeletal pain in military emergency department patients.

The null hypothesis is that 15 mg intramuscular ketorolac will be inferior when compared to 60 mg intramuscular ketorolac for the treatment of acute musculoskeletal pain in military emergency department patients.

#### 9.4 Study Design:

Describe study design in one to two sentences (e.g., prospective, use of existing records/data /specimens, observational, cross-sectional, interventional, randomized, placebo-controlled, cohort, etc.). Specify the phase – Phase I, II, III, or IV – for FDA-regulated investigational drug research

This study utilizes a single-blinded, randomized controlled non-inferiority trial design.

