#### 9.6 Benefit to the DoD:

State how this study will impact or be of benefit to the Department of Defense

It is the primary aim of the study to demonstrate that low dose intramuscular ketorolac, 15 mg, is not inferior to high dose intramuscular ketorolac, 60 mg, for the treatment of musculoskeletal pain. In proving the primary aim of the study, it is our hypothesis that the total man hours lost will decrease as a result of better pain management at the time of presentation to the emergency department. Second, by demonstrating that the lower dose is not inferior, this study may help increase patient satisfaction scores within military emergency departments. Lastly, by providing evidence with this single-blind, non-inferior study, it may be inferred that our results will add to the current set of literature which could become a pathway to building a larger multi-center study.

During his tenure, the previous Chief of Staff for the Army, GEN Mark Miley, clearly maintained that readiness is the priority of the U.S. Army. The military medical community is front and center in maintaining the DoDs level of readiness. This study aims to demonstrate that low dose intramuscular ketorolac is not inferior to high dose intramuscular ketorolac. By demonstrating non-inferiority, it is postulated that patients receiving the lower dose of ketorolac may experience a faster return to work period. This shorter period may equate to less man hours lost. This hypothesis is based on previously demonstrated higher incidents of dose related adverse events.

We anticipate that there will be a lower rate of adverse outcomes by utilizing lower doses of ketorolac. These findings result in multiple benefits to the DoD, service member, and beneficiary. First, by showing a lower rate of adverse outcomes, treating with the lower dose may improve readiness by decreasing lost man hours. Secondly, reducing the amount of adverse effects while maintaining the same level of therapy, patient satisfaction may improve, as well.

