#### Randomization and Study Subject Packet Creation

Fully enrolled subjects will be randomized based on a two block randomization generated by the website [www.graphpad.com](http://www.graphpad.com). Randomization will be created so there are two groups (two block randomization), one which will receive 15 mg of intramuscular ketorolac and one which will receive 60 mg of intramuscular ketorolac. Each group (block) will consist of 61 subjects per the power analysis described later in this document and will be assigned a Subject Study Number.

The Subject Study Number will be comprised of a "K" for ketorolac, "15" or "60" designating which dose of ketorolac will be administered and then a specific number reflecting their position within the randomization block (randomization block number). For instance, a Subject Study Number of "K15-30" would signify that this patient was randomized into the ketorolac 15 mg group and the number 30 would reflect both the block to which the patient was randomized and confirm that the patient is indeed in the 15 mg group. Using both "15" or "60" and the randomization block number acts as a checks and balance to ensure that the patient is randomized into the correct group, and that the subject receives the correct randomized dose. Based on the randomization block number it is possible to know into which group the subject was randomized, the dose of ketorolac which will be administered and the order of the patient in the overall randomization. Following randomization, Subject Study Packets will be prepared.

Subject Study Packets will be prepared prior to the data collection (prior to the screening process). These packets will be created using manila envelopes capable of containing all study documents and which can be sealed. The contents of the envelopes will include the (1.) Ketorolac Research Form, (2.) Informed Consent Form (which includes consent for a POC UHCG), (3.) HIPAA Authorization Form, (4.) pretreatment VAS form, and two post-treatment VAS forms. None of the documents utilized or created throughout the study will be entered in to the subjects EHR. The manila packet and all documents contained within it will be annotated with the Subject Study Number (as described above). A description of these forms is listed below.

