3. HIPAA Authorization Form: signature of this document authorizes investigators use of the subject's protected health information (PHI) and personally identifiable information (PII) responsibly, securely and only for the purposes of this study. PHI and PII will be explained in detail to the patient and all questions will be honored. Should the patient decline to sign this document, they will be excluded from the study.
  1. PHI: The only protected health information used for this study will be the (1.) chief complaint and (2.) vital signs. A review of systems (ROS) will be used for inclusion and exclusion purposes of this study, but the EHR will not be accessed for this information and this information will not be documented on any media. A detailed description of the ROS is provided later in this application.
  2. PII: The only PII used for this study will be the (1.) subject name, (2.) age (in years-not date of birth), (3.) medical record number (MRN) and (4.) gender.

4. VAS forms (pretreatment and post-treatment): these are single page forms with a 0-100 mm VAS. Four separate VAS forms will be included in the Subject Study Packet and will be used to assess the subject's pain prior to administration of ketorolac, and at the 30 and 60 minute intervals after ketorolac administration. A fourth form will be included in the event that the patient completes the VAS incorrectly. The subject in each instance and on separate forms, will be asked to mark a horizontal line on the 0-100 mm continuum indicating their pre-treatment level of pain and their pain level post-treatment at the 30 minute and 60 minute intervals. Three separate forms are utilized to control for response bias. The Subject Study Number will also be included on the document, but otherwise no other information will be contained on the VAS forms.

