#### Medication Administration

The primary investigator (PI) will maintain a resident-status through the Army-Baylor Doctor of Science Physician Assistant Studies Program for the entire research period of this study. The PI is a licensed physician assistant-certified and can under normal circumstances prescribe medication without approval by an attending physician. However due to the PI resident-status, all final treatment decisions (to include the ketorolac dosing used for this study) must be approved by a WBAMC ED attending provider.

For purposes of this study, the attending provider is usually a physician, but may be a physician assistant or nurse practitioner, and is the provider responsible for the subject's medical care at the time of data collection. Therefore, the attending provider is not a single individual. The PI may have a different attending provider for each shift or the attending may vary (being more than one individual) within one specific ED shift. Again, the attending provider is the final medical authority for every subject and it is the attending provider who will ultimately approve or disapprove ketorolac dosing regimens as they pertain to this study.

For instance, the PI may enroll and randomize a patient to the 15 mg ketorolac group. The PI will communicate this to the attending provider. However, the attending provider may reject the 15 mg dose and opt for a lower dose, higher dose or no ketorolac dose at all. For this reason, the inclusion and exclusion criteria for this study will document attending provider approval of the dosing regimen to which the patient is randomized prior to administration of the ketorolac.

The Regional Health Command Central (RHC-C) Human Research Protection Program was consulted on this issue specifically. Their guidance was that, for the purposes of this study, the attending physicians are not human subjects research in this study and do not require formal written consent to signify approval of the randomized ketorolac dose. However, they recommended that the PI obtain concurrence with the dose from the attending provider. The investigators for this study will have the attending provider sign the Ketorolac Research Form signifying their concurrence with the randomized dose.

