**Descriptive Statistics Data.**

Descriptive statistics data will be gathered to find correlation between subject demographics (age and gender) and location and duration of pain. These data will be obtained on the Ketorolac Research Form which is completed by the subject and will be included as descriptive statistics only. The data may or may not be analyzed for statistical significance, this will be at the discretion of the statistician. Furthermore, data pertaining to subjects requiring analgesia beyond the ketorolac used for this study, will also be collected for descriptive purposes only. Furthermore, data pertaining to subjects requiring analgesia beyond ketorolac, will be collected for descriptive purposes only. The data will be collected on the Ketorolac Data Collection Workbook, along with the other data.

At the completion of the entire data collection period for the entire study, VAS measurements will be obtained based on the methodology above and all data pertaining to the primary outcome (VAS scores), secondary outcome (adverse events) and descriptive statistics (from the Ketorolac Research Form) will be transcribed on to a Microsoft Excel work sheet. Any PHI or PII at this point will be de-identified and only the Subject Study Number will be used for identification. All paper documents will be secured in a manner previously described. The Excel worksheet is located on the PIs government issued common-access-card protected laptop. Access to this laptop requires both a common-access-card and a personal identification number (PIN) assigned to that specific common-access-card. The worksheet will therefore be highly secure and saved to the hard drive of the PIs laptop. The hard drive on the computer can only be accessed by the PI (as previously discussed) and network system administrators with permission. The AI for this research may also have a copy of the de-identified data, however, the data will be stored and secured in the exact same manner as the PI (common-access-card and PIN protected). All measures will be taken to protect the information of the study, however no PHI or PII will be stored on the Microsoft Excel work sheet.

**10.3 At any point in the study, will you request, use, or access health information in any form, including verbal, hard copy and electronic?**

Yes  No

**10.4 Review the definitions below and respond to the following two questions. If you are not sure of the answers, email [contact] for assistance.**

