#### **14.5 Privacy for Subjects:**

Describe the measures to protect subject's privacy during recruitment, the consent process, and all research activities, etc.

During the recruitment phase, the subjects' name, MRN, and Subject Study Number will be annotated on the master key. The master key will be a paper document which will be maintained by the investigator for the duration of the study. It will be secured in a padlocked locker within the WBAMC ED for the duration of the study.

The recruitment phase will be initiated in the waiting room by requesting them to step off to a more private, secluded portion, where they will be given the verbal synopsis (enclosed) by the PI or AI. Within this secluded portion, an enclosed room, within the Emergency Department the potential subject will complete the pre-screening and consent processes.

During the consent process, the study subjects will fill-out, sign, and date Informed Consent Form and HIPAA Authorization Form. These forms, with PII, will be maintained and secured in the same manner as the master key. The Subject Study Packets, containing the Ketorolac Research Form and VAS forms, will contain PHI but no PII as these forms will be annotated with only the Subject Study Number and will be de-identified (no PII will be on these documents). However, these forms will be secured in the same manner as the other forms.

Upon completion of the data collection phase, all forms will be transferred securely to WBAMC room 10015 and secured in a locked cabinet or locker, behind a locked door (secured with a cypher lock) for a minimum of two years following the completion of this study, in accordance with IRB and WBAMC policies.

The single electronic document will be the Excel worksheet used to compile all study subject data. The document will be located on the PIs government issued laptop. This worksheet will be password protected and saved to the hard drive of the PIs laptop. The hard drive on the computer can only be accessed by the person who saved it and network system administrators. All measures have been created to protect the information of the study though there will not be any PHI or PII on the document. This document will be destroyed upon completion of the dissertation defense.

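### The trial is called single-blind, but the dose is written into the study number on the forms the subject marks, and no step in Protocol 10.1 withholds it from the subject

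*Protocol*

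**What the plan says.** Protocol 9.4 gives the design in one sentence: "This study utilizes a single-blinded, randomized controlled non-inferiority trial design". Section 9.6 repeats the label ("by providing evidence with this single-blind, non-inferior study"). Neither place says who is blinded or how, and the SAP does not mention blinding.

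Section 10.1, under Randomization and Study Subject Packet Creation, defines the Subject Study Number as a K, then 15 or 60 "designating which dose of ketorolac will be administered", then a position in the randomization; K15-30 is the protocol's example. It continues: "The manila packet and all documents contained within it will be annotated with the Subject Study Number". The item on the VAS forms confirms this: "The Subject Study Number will also be included on the document, but otherwise no other information will be contained on the VAS forms".

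On the subject's contact with these forms:

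- The subject marks the VAS at baseline, 30 and 60 minutes (10.1 and 10.2).
- The subject circles adverse events on the Ketorolac Research Form (10.1). Section 10.2 says of the descriptive data: "These data will be obtained on the Ketorolac Research Form which is completed by the subject".
- Under 14.5, "the study subjects will fill-out, sign, and date Informed Consent Form and HIPAA Authorization Form".
- Under Medication Administration, the investigators will "have the attending provider sign the Ketorolac Research Form signifying their concurrence with the randomized dose".

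**The concern.** The primary outcome is the subject's own pain mark, and part of the secondary outcome is what the subject circles. For such outcomes, blinding the subject is the main protection against expectation affecting the result. Here the protocol claims that protection, but its own labelling rule puts the dose on the page where the outcome is recorded. This goes beyond an omitted detail: if staff follow 10.1 exactly, the dose code is in front of the subject. A report that then called the trial single-blind would claim more than the procedure secures.

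**Working it through.** The point turns on the text, and no figure in the sample-size section depends on it. Three questions need checking.

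**1. Who could the blinded party be?** Under Medication Administration, the investigator knows the randomized dose and tells the attending provider. The attending must agree to it and prescribe it, and the assigned nurse prepares and gives it. None of these is blinded. Nor does an assessor-blind reading work. Section 10.2 delays VAS measurement until all data are collected, but those who measure are the investigators, and the forms in front of them carry the dose code. The analysis worksheet also identifies subjects by the same number. That leaves the subject.

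**2. Which forms handled by the subject carry the code?**

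| Form | What the subject does | Carries the code? |
|---|---|---|
| VAS at baseline, 30 and 60 min (3) | Marks pain | Yes, stated for these forms in 10.1 |
| Ketorolac Research Form (1) | Completes it, circles adverse events | Yes, by the packet rule in 10.1; 14.5 agrees |
| Spare VAS (1) | Uses it only if a mark is invalid | Yes, as for the other VAS forms |
| Consent and HIPAA forms (2) | Signs | Yes by the packet rule in 10.1, but 14.5 points the other way |

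The undisputed count is 3 + 1 = 4 forms, or 5 with the spare. Under the packet rule in 10.1 it is 4 + 2 = 6, or 7 with the spare. The last row is uncertain because 14.5 describes the numbered packets as holding the Research Form and VAS forms, and treats the consent and HIPAA forms separately as documents with identifiers. Section 14.1 also reserves the link to the subject's name for the master key, which a numbered and signed consent form would defeat. The argument needs only the four.

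**3. Does any step in 10.1 withhold the dose?** The section runs from definitions through packet preparation, consent, dose concurrence, injection and the 60-minute assessment. It contains no neutral code, no instruction to keep the code or dose from the subject, and no instruction on preparing the syringe out of view. The attending's signed concurrence with the dose is placed on a form that the subject also completes.

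For the code to unblind a subject, the subject must know the two doses. Sections 13.1 and 13.4 promise a synopsis and a consent discussion that cover the objectives, and the purpose in 9.3 names 15 mg and 60 mg. Disclosure is therefore likely, though the documents available do not show it. With it, K15 or K60 needs no key.

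**The case against.** The strongest reply is that unblinding is inferred. The consent form, the verbal synopsis and the forms themselves are not in the public copy. A small code in a corner may go unnoticed, and the consent text may tell subjects that the dose will be withheld. This stands as a limit on how often the code would be read. It does not restore the blinding, because such a statement would leave the code on the forms, and 10.1 is the step-by-step procedure where masking would have to be carried out.

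A second reply is that the dose in the number has a purpose: 10.1 presents it as a check that the right dose is given. That is true, and any fix must keep the check. It does not require the code to be on subject-facing forms.

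A reader might also infer three stronger conclusions that the documents do not support:

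- **That injection volume reveals the dose.** Section 9.2 lists vial strengths as background, but section 18.2 does not say which is used. Each subject has one injection and nothing to compare it with. Section 10.1 neither requires nor rules out drawing up out of view.
- **That unblinded subjects seek rescue, are unenrolled, and so bias the result towards 15 mg.** Under Medication Administration, additional analgesia is decided by the attending provider, who knows the dose. Dose-related rescue could therefore occur with perfectly blinded subjects, and masking the subject addresses that path only in part.
- **That a definite amount of power or type I error is lost.** Such figures can be computed for any assumed shift in VAS, but no shift has a source in the documents. They would show how sensitive this sample size is to bias in general, and would say nothing about how large this problem is.

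**Conclusion.** The point holds. The protocol claims single-blinding, only the subject can be the blinded party, and a stated rule puts the dose code on at least four forms the subject fills in, including all three scheduled primary-outcome forms. No step in 10.1 offsets this.

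The textual conflict is certain. Its effect rests on two assumptions: that subjects are told both doses, and that some notice the code. The number who would, and the size and direction of any bias, are unknown, and the effect may be negligible if few notice. The text does not support calling the trial open-label in practice or saying its result is biased. It does support saying that the claimed blinding is not secured for a self-reported outcome. The change should be made because it is cheap, with medium confidence that it matters to the result.

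**What to change.** In 10.1:

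1. Name the subject as the blinded party.
2. Use a sequential number with no dose in it on the envelope and on every subject-facing form.
3. Keep a number-to-dose list, and move the dose check and the attending's concurrence signature to a separate slip that the subject does not see.
4. Instruct staff not to state or show the dose to the subject before the 60-minute VAS, and to draw up out of view where practical.

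Syringe sleeves and a question asking the subject to guess the dose after the 60-minute VAS are optional.

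The edit is wider than one paragraph. The number is also used in the VAS form description, the master key and the injection step in 10.1, and in the worksheet described in 10.2. The concurrence signature under Medication Administration moves as well. All need conforming changes. Beyond that, the cost is renumbered packets, one extra slip and a short briefing for whichever nurses and attending providers are on shift. The safety check moves to the slip and is not lost. Doses, sample size and analysis stay as they are.
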